9. NCORP PRACTICE SITE RANDOMIZATION

A practice site is defined as any practice location within an overarching NCORP designation where oncology physicians and study staff work independently, i.e., do not cross over into another site. Practice sites will be randomized to one of the two study arms by means of a computer-generated randomization table. The randomization process will be determined using R software provided by [name], the lead biostatistician of the URCC NCORP Research Base.

Sites are randomized on a continual basis due to a variety of factors (i.e., a new NCORP Community Affiliate has been added to the URCC NCORP Research Base network, a new oncology practice site has been added to an existing NCORP Community Affiliate, or an oncology practice site that is currently affiliated with an NCORP Community Affiliate has expressed interest in participating in the COACH study). Past accrual to URCC studies (or NCORP Cancer Control studies if URCC accrual information is not available for new Affiliates and sites) is used to stratify each practice site as a **large** accruing (20 or more accruals/year) site or a **small** accruing (less than 20 accruals/year) practice site in order to assure balance in the randomization. The general assumption will be that any new site will be considered "small", unless it is determined based on past accruals that they are large. For new oncology practice sites that meet the definition for being independent (i.e., physicians and staff that do not cross over into another site), the next unassigned randomization allocation, from the randomization table will be used to assign their study arm. The randomization table takes into account size of the practice site. If a new oncology practice site is added at a later time during the study with physicians/staff that also see patients (cross over) at both or multiple practice sites, the new practice site will be assigned to the same study arm as the already randomized practice site where the physician/staff also sees patients.

Once sites have IRB approval on file with the Research Base and at least one member of research staff is trained on all study procedures, they are notified of their randomization allocation by an email from the study PI, [name]. Practice sites names and randomization assignments are saved in the database, this is used to link to which arm each study patient belongs to during patient registration.

The original sample size calculation (Section 15) was based on the randomization of the 16 NCORP oncology practice sites. During study startup, as the structure of the new NCORP affiliates unfolded, more practice sites than was anticipated were interested in participating. The original protocol included the ability for more sites to participate, since the increase in the number of the clusters also increases the statistical power of the study.

[figure not shown]
10. INTERVENTION OVERVIEW FOR PHYSICIANS

Practice sites will be notified if they are in the intervention arm by URCC Research Base staff. Prior to the intervention, oncology physicians will receive training on how to best utilize GA information in clinical practice for older adults with cancer. The training session provides a brief overview of the intervention information and can be completed through a web conference, telephone call, or as a paper “sign-off” documenting review of the materials. The training materials were developed with resources from Drs. [name]’s and [name]’s geriatric oncology lectures.

The CRAs and/or research nurses at sites randomized to the intervention arm will be trained to utilize the [mycarg.org website](http://mycarg.org) to derive a summary of GA scores and a list of targeted GA-driven recommendations.

This information will be printed by the site CRAs for the oncology physician who will “sign off” that he/she has received and reviewed the information. Study or clinical staff can assist the physician in checking which recommendations were considered and facilitating implementation of GA-driven recommendations. Two copies of the summary and checklists should be made: one should be provided to the patient/caregiver and one should be retained in the study chart. Patients and caregivers should be provided with a copy of the GA summary and GA-driven recommendation forms prior to the audio-recorded visit. The original forms should be submitted to the URCC Research Base.

11. OUTLINE OF STUDY-SPECIFIC PROCEDURES

11.1. Procedures Prior to Screening Visit

11.1.1. Oncology Physician Enrollment and Participation

11.1.1a. If an oncology physician is interested in the study and meets the inclusion/exclusion criteria, he/she will agree to participate on paper or through REDCap (sent by the URCC Research Base).

11.1.1b. The oncology physician will complete a baseline survey on demographics and treatment preferences either on paper or through REDCap.

11.1.1c Ideally oncology physicians are enrolled as soon as possible. However, an oncology physician can be enrolled after his/her patient is identified for the study or prior to screening registration for the first identified patient.

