1.10. Study Subjects

The study involves adult human subjects.

NCORP practice sites will be randomized within a 2-arm cluster randomized design utilizing NCORP practice sites as the unit of randomization. A NCORP practice site will be defined as any practice location within an overarching NCORP designation where oncology physicians and study staff work independently (i.e., do not cross over into another practice site).

Study subjects will include:

- **Oncology physicians** at NCORP practice sites

- **Patients** will complete surveys and will also agree to have a clinical consultation with an oncology physician audio-recorded (baseline visit). Patients will have advanced cancer and various levels of functional status. Patients will be asked to identify a caregiver who may choose to participate in the study. As much as possible, caregivers should be recruited to be part of the study when the patient is recruited. In the rare circumstance that there is no willing caregiver to participate, the patient will be allowed to participate without a caregiver.

- **Caregivers** must enroll in the study before or on the baseline visit because they will accompany the patients during the clinic consultation that will be audio-recorded (baseline) and complete surveys.

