5.2. Oncology Physician Recruitment

Because oncology physicians are being recruited and enrolled from sites across the country by the URCC Research Base, oncology physicians will read and agree to participate either via Research Electronic Data Capture (REDCap) or on paper if REDCap is not a feasible option. REDCap is a software toolset (see Section 16.3 for more information) for electronic collection and management of research and clinical trial data developed by Vanderbilt University. Oncology physicians will be enrolled prior to enrolling (screening registration) their first eligible patient. Staff from the URCC Research Base (including the PI) will be available to answer any questions the oncology physicians may have over the phone. Procedures for the oncology physicians are minimal risk and involve: completing surveys that will be de-identified, and identifying patients for the study.

Oncology physicians will provide baseline demographic information, fill out a baseline survey that evaluates preferences for decision-making, and help identify their own patients who may be eligible for the study. The baseline survey can be completed online via REDCap or on paper if REDCap is not feasible. REDCap will securely store the oncology physician's email address for surveys. In addition to the email address, the only personal identifying information the oncology physicians will provide will be their name, age, ethnicity, and the name of the clinic where they work. The oncology physician will be assigned an ID number, which will be used to link their surveys together with those of patients enrolled in the study.

The oncology physician also will agree to have one visit per each patient audio-recorded (baseline). All parties present for recorded office visits, including: enrolled patients, any accompanying caregivers, family or friends, the oncology physician, and any other physicians or health care providers not participating in the study will be fully aware that the conversation is being audio-recorded and will provide verbal assent immediately before any recording begins, in addition to the prior written consent of enrolled subjects. These audio-recordings will be labeled and stored using the patient's initials and date.

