6. REGISTRATION

6.1. Prior to entering participants (i.e., oncology physicians, patients, caregivers) on this protocol, the following must be on file at the URCC NCORP Research Base:

6.1.1. Documentation of IRB approval in the form of an HHS Protection of Human Subjects Assurance Identification/IRB Certification/Declaration of Exemption (formerly Form 310), CTSU approval form or signed letter from the IRB.

6.1.2. A copy of the institution's IRB-approved informed consent document.

6.1.3. Written justification for any substantive modifications made to the informed consent concerning information on risks or alternative procedures.

These documents are submitted to:
[contact]

OR

[name]
URCC NCORP Research Base
[name]
[name]
[name]
[name]

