## **3 Study Methods**

### **3.1 General Study Design and Comparators**

[figure not shown]
The study design is a cluster randomized clinical trial. The intervention is designed to try to improve communication about age related concerns between oncology physicians, patients and their caregivers. Study subjects include oncologists, patients and their caregivers. Sites within the URCC

NCORP network are randomized prior to the enrollment of any subjects at any site. Sites in both arms (control and intervention) will conduct the GA on all subjects. Physicians at sites randomized to the intervention arm will be provided with a GA summary and GA-driven recommendations. Since the GA is not part of community oncology physicians’ standard of care, a usual care comparator arm is appropriate and will allow for the accurate and appropriate assessment of how the intervention can improve communication about age-related issues and outcomes compared to current clinical practice. This study design is similar to previous studies that evaluated the impact of providing summarized HRQoL information to patients and oncology physicians on communication and outcomes. Usual care was the comparator arm in these cluster randomized studies.

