Though the COACH study sample size is 528 patient/caregiver dyads, there is no cap on the number of physicians enrolled. A total of 2 participants withdrew between screening and their baseline visit. Of the 413 patients enrolled, 159 have completed the study and all study requirements, 21 completed the study with some missing data, and 101 are still active. To date of the patients enrolled 48 withdrew, 61 expired, 21 their status is being determined and 4 participants are lost to follow-up. Due to the frailty of the subjects in this population, it is not

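### Physicians can decide whether to join after their site has been told its arm, so the physicians whom patients rate may differ between arms

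*Protocol*

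**What the plan says.** The design is cluster randomised, "utilizing NCORP practice sites as the unit of randomization" (Protocol 1.10). SAP 3.1 states that sites within the "NCORP network are randomized prior to the enrollment of any subjects at any site", and the same section says "Study subjects include oncologists, patients and their caregivers". Physicians are therefore among those enrolled after randomisation.

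Protocol 9 sets two conditions for telling a site its arm: IRB approval on file, and at least one research staff member trained. Once both are met, "they are notified of their randomization allocation by an email from the study PI". Neither condition involves a physician having agreed.

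Protocol 6.1 lists IRB documents that must be on file "Prior to entering participants (i.e., oncology physicians, patients, caregivers) on this protocol". The latest time for a physician to join is given in Protocol 5.2: "Oncology physicians will be enrolled prior to enrolling (screening registration) their first eligible patient". Protocol 11.1.1 describes opting in by interested physicians. It prefers early enrolment but adds that "an oncology physician can be enrolled after his/her patient is identified for the study or prior to screening registration for the first identified patient". SAP 3.4.1 notes that "there is no cap on the number of physicians enrolled". Under Protocol 11.1.2a, only patients of enrolled physicians can be registered.

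**The concern.** Randomising sites balances, in expectation, the physicians who work there. It does not balance the physicians who choose to join once the arm is known. Both arms ask a physician for surveys and a recorded visit. Arm 1 also asks for a training session (Protocol 10) and for review and signature of the summary and recommendation forms for each patient (Protocol 11.3.2). If physicians already attentive to ageing join more readily in one arm, the arms differ before the intervention has done anything.

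This would reach the result directly. HCCQ-age measures the oncology physician's behaviour and communication about age-related concerns (Protocol 7.1), and the discussion count is taken from that physician's own consultation (Protocol 15.3). The first is the NCI primary outcome. The second is Secondary Aim 1, which is PCORI's primary outcome. The problem is separate from selection of patients: it would remain if every eligible patient of every enrolled physician were approached.

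**Working it through.** **Timeline, from the documents**

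1. The site is randomised before its subjects, including physicians, are enrolled (SAP 3.1).
2. IRB documents reach the Research Base. Only then can physicians be entered (Protocol 6.1). This is also one of the two conditions for notification (Protocol 9).
3. One staff member is trained, and the site is told its arm (Protocol 9).
4. Physicians may join at any time from step 2 until screening registration of their first patient (Protocol 5.2, 11.1.1c).

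The only window for enrolment without knowledge of the arm lies between steps 2 and 3. Nothing requires physicians to use it.

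**Can the planned analysis detect or remove an imbalance?**

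- In Appendix X-1 Table 1, HCCQ-age is first collected at the Telephone Team Call, after the intervention visit. There is no earlier value to adjust for.
- The model has a random site effect and no physician level (Protocol 15.2). A site effect does not remove a shift common to a whole arm.
- The only physician-level term is oncologist type, which is not defined (Protocol 15.1, SAP 4.1).
- The screening log covers patients and caregivers (Protocol 11.1.2b). The input tables in SAP Appendix C have patient and caregiver rows only.

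**The plan's own figure**

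Inputs from Protocol 15.2: SD 2.1, ICC 0.14, 8 sites per arm, 31 patients per site, significance level 0.05, power 80%.

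- Design effect = 1 + (31 − 1) × 0.14 = 5.2
- SE = 2.1 × √(2 × 5.2 / (8 × 31)) = 0.430
- Detectable difference, two-sided noncentral t with 14 df = 1.296, against the stated 1.3. Reproduced.

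**Illustration of size**

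The documents give no between-physician SD and no figure for an imbalance. I use the between-site SD as a yardstick and assume a shift of 0.25 to 0.5 of it, with no true intervention effect.

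- Between-site SD = 2.1 × √0.14 = 0.786
- Shift = 0.25 × 0.786 = 0.196, to 0.5 × 0.786 = 0.393 points
- Share of the 1.3 target = 0.196/1.3 = 15%, to 0.393/1.3 = 30%

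For 68 sites (the participating number in Protocol 15.2), take 34 per arm and 16 × 31 = 496 patients, so 496/68 = 7.29 per site.

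- Design effect = 1 + 6.29 × 0.14 = 1.88
- SE = 2.1 × √(2 × 1.88 / 248) = 0.259

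Probability of a significant result favouring Arm 1 (2.5% with no shift):

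| Assumed shift (points) | 16 sites, SE 0.430, 14 df | 68 sites, SE 0.259, 66 df |
|---|---|---|
| 0.196 | 6.3% | 11.3% |
| 0.393 | 13.4% | 32.2% |

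Adding sites narrows the standard error but leaves the shift where it is, so the same shift is more likely to be declared significant.

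**The case against.** The strongest reply is that late joining is permitted, not prescribed. Protocol 11.1.1c says physicians should ideally be enrolled as soon as possible, and some could agree between IRB approval and staff training. The extra work in Arm 1 is also modest: training is brief and can be a paper sign-off, and staff may help with the forms (Protocol 10, 11.3.2). Both points stand. A reader might infer that physicians as a rule joined knowing their arm, or that the results are already biased towards Arm 1. The documents support neither: they show an open route, not its use, and say nothing about direction.

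The plan also has relevant material. Oncologist type is in every regression. Physicians complete a baseline survey covering practice details, patient volume, years since training and decision-making preferences (Protocol 5.2, Appendix X-1 section 4). Protocol 15.4.3 adds baseline physician preferences to an exploratory model of discussions and uses baseline and follow-up physician forms to study confidence. SAP 5 promises a CONSORT diagram for providers. These could reveal an imbalance and partly adjust for it. They do not prevent one, and neither document plans to compare these data by arm or to use them in the main analyses. A survey completed after notification may also be coloured by knowledge of the arm.

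The numbers invite two fair criticisms. A between-site SD is not a between-physician SD. The 68-site column assumes independent, equal-sized clusters, whereas the sample table in SAP Appendix A shows many rows sharing one randomisation ID and arm, which suggests fewer independent units. For that reason the 16-site column stands beside it, and neither is an estimate.

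Blinding of the Telephone Team and the coders is no answer here: it protects measurement, not who joined.

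**Conclusion.** The point holds as a design weakness. Physicians can decide whether to join after their site knows its arm, no step fixes the physician list first, and both the HCCQ-age comparison and the discussion count depend on who joins. Whether an imbalance arose, how large it is and which arm it favours cannot be learned from the documents. The rates of 6% to 13% (16 sites) and 11% to 32% (68 independent, equal-sized sites) are conditional on an assumed shift of 0.2 to 0.4 points towards Arm 1. They show that a shift well below the 1.3-point target would matter, and should not be read as the trial's error rate. The study schema is a figure not available to me, so any ordering shown there is unchecked.

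**What to change.** 1. **Protocol 9 and 11.1.1, sites not yet notified.** Release the allocation only after the site has submitted a list of physicians who have agreed to take part, and flag any who join later. Sites are still randomised on a continual basis, so this can help, but its reach is limited: SAP 3.4.1 already reports 413 enrolled and, elsewhere in the section, 479 evaluable patients, against a target of 528.
2. **SAP 4, all sites.** Compare the physician baseline survey by arm: practice details, patient volume, years since training, decision-making preferences, and baseline confidence items where asked. Add a sensitivity analysis of HCCQ-age and of the discussion count adjusted for these. State that surveys completed after notification may themselves reflect knowledge of the arm. With accrual this far on, this step carries most of the weight.
3. **SAP 5 and Appendix C.** Flag each physician as enrolled before or after the site's notification date, and report the counts by arm in the provider CONSORT diagram. Run an analysis restricted to physicians enrolled before notification only if that group is large enough; it may be very small, because IRB approval both opens physician entry and is a condition for notification.

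The cost is slightly slower activation of the remaining sites and a little extra analysis. No new patient data are needed. Step 3 depends on physician enrolment and site notification dates being held in usable form; the Research Base should have them, but the documents do not confirm it.

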11.1.2. Subject Identification Process

11.1.2a. Patients: Once a site is IRB approved, the site study staff can start screening for patients according to the inclusion/exclusion criteria for patients (Section 4.2). Only patients from enrolled physicians can be registered.

11.1.2b. Screening Log: A screening log will be kept at each participating site, where *both* patients and caregivers approached for the study will be entered by site study staff.

11.2. Screening: VISIT 0

11.2.1. Patient & Caregiver Recruitment & Consent Process

11.2.1a. Patients

- The site study staff will notify the patient's oncology physician when a patient is identified as a possible candidate for the study. Site study staff should screen for patients who may fit eligibility criteria for all requirements other than GA impairment. It is anticipated that some of the patients who are eligible will be new patients for the oncology physician.
- The oncology physician and/or CRA should mention the study to the patient and give out recruitment materials.
- If the patient is interested, the oncology physician and/or site study staff will explain the study and once all aspects of the study have been discussed to the patient's satisfaction, the voluntary written informed consent procedures will be completed with the patient if they choose to enroll in the study.
- Patients should choose a caregiver to participate. As much as possible, caregivers should be recruited to be part of the study when the patient is recruited. In the rare circumstance that there is no willing caregiver to participate, the patient will be allowed to participate without a caregiver. URCC Research Base staff should be notified prior to patient registration if there is no designated caregiver.
- The site study staff can schedule a separate visit with the patient and/or caregiver to go over the consent and initiate study procedures if more time is needed.

11.2.1b. Caregivers

- If a caregiver, chosen by the patient, is interested in the study and meets the inclusion/exclusion criteria, the site study staff will confirm eligibility (as per section 4.3) and complete the informed consent procedures with the caregiver. Caregivers must enroll in the study before or on the baseline visit.

11.2.2. Patient & Caregiver Assessment Process

11.2.2a. Once a patient has consented, screening and baseline assessments/procedures can occur. Site

study staff can schedule a separate visit with the patient and caregiver to complete study procedures if more time is needed.

11.2.2b. The procedures for screening will consist of the steps below:

- Confirm that the patient’s oncology physician has been enrolled onto the study and if not, follow procedures for enrolling oncology physicians.
- Patients meeting eligibility criteria are initially registered with a screening registration after signing consent.
- Administer Cognitive, Physical, and Nutritional Assessments to the patient.
 - These assessments can be administered right after consent, at a separate visit scheduled by site study staff, or just prior to the next oncology physician visit. Allow 45 minutes to perform assessments if done just prior to an oncology physician visit.
 - Anyone at the practice site can administer cognitive and physical assessments to the patient as long as they have participated in the required GA training administered by the URCC Research Base. CRAs, clinical nurses, and technicians are all eligible to participate in training and can complete GA study procedures.
- Patient will complete all screening surveys.
 - Ideally the patient will complete either at the time of consent or the screening and baseline packets can be taken home and completed before the next visit with the oncology physician. If the patient needs assistance from site study staff to complete surveys, allow adequate time. Approximately 60 minutes is recommended.
- Abstract required medical information from chart.

11.2.2c. The GA must be completed prior to the study visit with the oncology physician. The study visit with the oncology physician will be audio-recorded with the oncology physician and patient. The caregiver should be encouraged to attend this study visit, but the study visit can occur without the caregiver present if the caregiver is not available.

11.2.2d. The procedures for the caregiver assessments will consist of the steps below:

Caregivers will complete all baseline surveys. Caregivers will complete either at the time of consent or the packet can be taken home and should be completed before the next visit with the oncology physician.

11.3. Baseline: VISIT 1

